**c. Exclusion criteria**

The exclusion criteria are the following:

- Not having given their free consent to participate in the study
- Present a serious comorbid mental disorder, associated intellectual disability, history of severe brain damage or neurological disorder that may function as a confounding factor (Associated organic type disorder, borderline or lower intellectual IQ)
- Active substance abuse (except nicotine)
- Have a cochlear implant, fixed hearing aids or head plates.
- Having suffered a concussion to the head with loss of consciousness that subsequently triggered symptoms related to the pathology.
- Suffering from epileptic seizures.
- Not having the desire to participate in dance therapy sessions for any reason or to undergo EEG-type tests.
- Be currently involved and participating in another cognitive rehabilitation program.

**d. Criteria provided for the withdrawal of subjects from the study**

These criteria are:

- Explicit request from the person to stop participating in the study.
- Change of place of residence, outside the autonomous community in which the study will be carried out.
- Death of the person.
- Worsening of pathological symptoms or hospital admission during the

study.

- Medical findings, such as epilepsy, during the EEG.

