## **3. Secondary objectives**

- 1) To compare the scores obtained from the neurocognitive test battery between the experimental group and the control group.
- 2) To compare the changes in brain activity patterns recorded by electroencephalography between the experimental group and the control group.
- 3) To analyze the changes generated in both groups in order to be able to identify the

possible correlations between the improvement in cognitive functions and the alterations in brain activity.

- 4) To evaluate the effects of a 20-session dance therapy program on the symptomatology of people with SMD using the PANSS (later presented in the section on data collection).

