## **STUDY METHODOLOGY**

### **1. Design**

A single-centre prospective randomised controlled trial will be conducted with a minimum of 47 patients with severe mental disorder (SMD) who will be randomly assigned into two groups, 1 intervention group receiving dance therapy (n=26) and 1 control group who will not receive any intervention or added treatment apart from continuing with their usual treatment (pharmacological), but will not receive intervention with dance therapy (n=21).

In summary, the groups are:

- Experimental group (n=26): people with SMD receiving dance therapy.
- Control group (n=21): people with SMD who do not receive the dance therapy intervention but do receive their usual pharmacological treatment.

Tests will be administered before the start of the study and at the end of the study, as well as 3 months after the end of the study in order to compare the results between groups.

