intervention program with dance therapy with the experimental group. In particular, to find the standard deviation of our control group sample with severe mental disorder, the mean values of the negative symptoms of the PANSS scale were chosen again (as they show significant statistical differences in scores between the control group and the experimental group in the manuscript of Chao & Xiaolin, 2022). In this case, the control group presented a mean of 14.98 on negative symptoms before the parallel start of the dance therapy intervention program, and a mean of 11.32 after the conclusion of the dance therapy intervention stage in the experimental group. Considering these means, we proceeded to calculate the sample standard deviation with the same procedure and software previously used to find the standard deviation of the intervention group in the previous point. Here we obtained a value for the sample standard deviation of our control group of 2.588.

In addition to the above, as the starting hypothesis is that the dance therapy program will improve emotional management and increase cognitive performance, it can be assumed that the minimum response to the program will be double (2).

After performing the mathematical calculation, accepting an alpha risk of 0.05 and a beta risk of 0.2 in a unilateral contrast, 28 participants in the intervention group are required to detect a difference equal to or greater than 2,822 units, as well as 28 participants in the control group to detect a difference equal to or greater than 2,588 units.

In addition, an expected rate or proportion of loss to follow-up of 10% ( $10/100=0.1$ ) due to experimental errors, drop-out, etc., has been estimated in the intervention group, with participants engaged in the dance therapy intervention. On the other hand, a loss-to-follow-up rate or proportion of 25% ( $25/100=0.25$ ) has been estimated in the control group with participants not engaged in the dance therapy intervention. This expected increase in losses in the control group is based on the hypothesis that the patient who does not receive the intervention may not be as involved in the experiment or, eventually, debut with pathological manifestations associated with their medical condition leading to absenteeism or indisposition during the data collection stage.

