## **PROCEDURE or DESCRIPTION OF THE STUDY**

### **1. Workplan**

All the tests (BASC, MoCA, PANSS and EEG) will be carried out with the 47 patients with SMD to find out their baseline status. The people with SMD will be randomly assigned to an experimental group (dance therapy program) or a control group (without intervention in dance therapy but with regular pharmacological treatment). The study will last approximately 1 year between the administration of tests, the program and the analysis of results. The dance therapy program will last 20 sessions over 10 weeks. The sessions will take place at the headquarters of the Asociación Canaria de Terapias Creativas (ASCATEC) in the Siglo XXI space in Santa Cruz de Tenerife.

The 26 people with SMD in the experimental group will participate in a 10-week intervention program with 2 sessions per week in which they will work for 1 hour on memory, attention and executive functions through dance and movement, ending with 10 minutes of Mindfulness.

The 21 people in the control group will not receive any type of dance therapy intervention, but will continue with their usual pharmacological treatment.

The effects will be measured after a treatment of 20 sessions (twice a week). Results will be obtained by analyzing EEG parameters (EEG amplitude and frequency) and cognitive functions (BACS and MoCA). On the other hand, at the end of the 20-session program, tests will also be administered to assess the symptomatology of the severe mental disorder suffered by the person (PANSS) to assess the effects of the program on these variables.

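### Withdrawal from the study for worsening or admission would, on its natural reading, leave later PANSS values missing for a reason tied to PANSS itself; the size is unknown and may be near zero

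*Combined protocol and SAP*

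**What the plan says.** Section 2.d is headed "Criteria provided for the withdrawal of subjects from the study". Beside the participant's own request, relocation, death and medical findings on the EEG, it lists "Worsening of pathological symptoms or hospital admission during the" study. The list is not limited to one arm, and it gives no threshold, scale or assessor for worsening.

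The control arm has no study treatment that could be stopped. The Design section describes "1 control group who will not receive any intervention or added treatment apart from continuing with their usual treatment", and the Workplan adds that "The 21 people in the control group will not receive any type of dance therapy intervention".

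Symptoms are an outcome. Secondary objective 4 is "To evaluate the effects of a 20-session dance therapy program on the symptomatology of people with SMD using the PANSS". The Study variables section names PANSS as the secondary variable. Data Collection schedules the tests at baseline, at the end of the programme and 3 months later.

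Section 2.e expects a 10% loss "due to experimental errors, drop-out, etc., has been estimated in the intervention group" and, for controls, "a loss-to-follow-up rate or proportion of 25" per cent. It explains the higher control figure by lower involvement, or by patients who "debut with pathological manifestations associated with their medical condition leading to absenteeism or indisposition during the data collection stage".

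The statistical analysis section names rank tests (Mann-Whitney, Kruskal-Wallis, Wilcoxon, Friedman) followed by mixed models. It states no analysis set, no rule for missing data and no sensitivity analysis.

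**The concern.** If a patient whose symptoms worsen leaves the study and is not tested again, the later PANSS values are lost because of the quantity PANSS measures. The patients still observed are then, on average, those who did better.

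The planned methods do not fully deal with this. The rank tests use only observed or complete values. The mixed model uses what was recorded before the patient left, and it is valid if loss depends only on recorded data. Worsening between two visits that triggers withdrawal is never recorded as a PANSS score.

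At stake is the PANSS comparison at the end of the programme and at 3 months. If such losses fall mainly in controls, the only arm for which section 2.e names illness, any benefit of dance therapy is understated. If they fall mainly in the dance arm, benefit is overstated or harm is hidden. The main outcomes, cognition and EEG, are touched only as far as they correlate with worsening.

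**Working it through.** **Does 2.d end assessment?** No sentence says so. Three things point that way: the heading speaks of the study and not of the sessions; the rule covers controls, for whom there are no sessions to stop; and no section plans an assessment after withdrawal. Against it, the 3-month tests are scheduled without any stated exception. The natural reading is that assessment ends, but it remains an inference.

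**The plan's own loss figures.** Section 2.e starts from 28 per arm. Dance: 28 × 0.10 = 2.8 lost, leaving 25.2, which the plan gives as 26. Control: 28 × 0.25 = 7 lost, leaving 21. These are total losses for all reasons and are not tied to a visit.

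**Completer bias, patients removed by end value.** Assume normal PANSS scores with SD 1, the full loss rates applied to one visit, a share f of the losses being the worst scores, and the rest random. Removing the worst fraction q makes the observed mean look better by φ(z₁₋q)/(1−q), with q = 0.10f for dance and q = 0.25f for control.

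| Share f | Dance | Control | Net, against dance |
|---|---|---|---|
| 1/4 | 0.058/0.975 = 0.060 | 0.123/0.9375 = 0.131 | 0.07 SD |
| 1/2 | 0.103/0.95 = 0.109 | 0.206/0.875 = 0.235 | 0.13 SD |
| all | 0.175/0.90 = 0.195 | 0.318/0.75 = 0.424 | 0.23 SD |

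If the worst-case losses occur only in the dance arm, the dance column alone applies and the sign reverses: 0.06, 0.11 or 0.20 SD in favour of dance.

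**Completer bias, patients removed by worsening.** The criterion speaks of worsening, which is a change from baseline. With baseline correlation ρ and equal variances, the shift in end scores is the tabled value × √((1−ρ)/2), and the shift in change scores is the tabled value × √(2(1−ρ)). With all losses of this kind and equal shares:

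- ρ = 0.5: end scores 0.229 × 0.500 = 0.11 SD; change scores 0.229 × 1.000 = 0.23 SD.
- ρ = 0.7: end scores 0.229 × 0.387 = 0.09 SD; change scores 0.229 × 0.775 = 0.18 SD.

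The analysis section does not say whether end scores or changes are compared, so both are shown. The documents give no correlation; 0.5 and 0.7 are assumptions.

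**Mixed model.** This was simulated with all baselines kept and, within each arm, the end value regressed on baseline. With all losses worst-case and equal shares, the net bias left is about 0.20 SD (ρ = 0.5) or 0.16 SD (ρ = 0.7) for removal by end value. For removal by change it is about 0.20 or 0.17 SD. Adjustment lowers the 0.23 SD modestly in the first case. In the second it does not help an end-score comparison at all.

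**Finite samples**, removal by end value, all losses worst-case in both arms. With 28 per arm and the worst 3 and 7 removed, the net bias is 0.21 SD. With 26 and 21, the numbers assigned in the Design section, and the worst 3 and 5 removed, it is 0.18 SD.

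**Scale.** The standard error of a difference with 26 and 21 patients is √(1/26 + 1/21) = 0.29 SD.

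**Cognition.** The shift is the correlation with worsening times the PANSS shift. At an assumed 0.2 to 0.4, with all losses and equal shares, this is 0.2 × 0.229 = 0.05 to 0.4 × 0.229 = 0.09 SD.

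**The case against.** The strongest reply is that 2.d lists grounds for withdrawal and never says that testing stops or that collected data are discarded. That is right. A reader might infer that the plan orders assessments to end; the documents support this only as the natural reading of an ambiguous rule.

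Second, the 10% and 25% are not losses caused by 2.d. Section 2.e attributes them partly to experimental errors, drop-out and low involvement, and the illness it mentions would keep some patients away whatever 2.d said. This stands. A reader might take 0.23 SD, or the 0.42 SD obtained if every control loss and no dance loss is a worst case, as the expected bias. Both contradict the plan's own mixed reasons for loss, and the second also assumes no worsening-related loss among dance patients. They are outer limits. When patients leave by worsening and end scores are compared, 0.42 SD itself falls to 0.21 SD (ρ = 0.5) or 0.16 SD (ρ = 0.7).

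Third, PANSS is secondary, and the direction section 2.e suggests works against dance therapy, so it would not create a false claim of benefit. This lowers the priority. It does not settle the matter, because nothing in the documents rules out worsening in the dance arm, where the error would hide harm.

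Fourth, the rule may protect participants, and testing someone who is acutely unwell is not always possible. This limits how much data can be recovered. It is no argument against testing those who consent and are able.

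The missing analysis set and missing-data rule are general gaps that exist whatever 2.d means. They matter here because nothing else in the plan compensates for loss related to worsening.

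**Conclusion.** The point holds as a modest one. Read naturally, 2.d removes patients from follow-up, in both arms, for a reason tied to a secondary outcome, and the planned analysis does not fully correct for that.

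The size attributable to 2.d is unknown and may be near zero, because the documents give no rate of worsening. If a quarter to a half of the planned losses are worst-PANSS cases in both arms, the illustration gives 0.07 to 0.13 SD against dance (removal by end value, end scores compared). With all losses of that kind and equal shares, the upper limit is 0.23 SD for removal by end value. For removal by worsening it is about 0.09 to 0.11 SD in end scores or 0.18 to 0.23 SD in change scores. A baseline-adjusted mixed model leaves about 0.16 to 0.20 SD. All these equal-share figures are below one standard error (0.29 SD), and the direction reverses if such losses fall mainly in the dance arm. They rest on assumed normality, assumed shares, assumed correlations and full loss at a single visit.

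A reader might conclude that the main cognitive and EEG comparisons are compromised. The documents do not support that: the effect there is indirect and smaller, and depends on a correlation they do not give. This is an improvement to consider, not a defect that invalidates the trial.

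**What to change.** In section 2.d, state that withdrawal for worsening or admission does not by itself end outcome assessment. Patients who still consent and can be tested keep their scheduled end-of-programme and 3-month assessments. No clinical decision changes.

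In the statistical analysis section:

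- analyse all randomised patients in their assigned arm;
- report reasons for loss by arm and visit;
- add one simple sensitivity analysis for PANSS values lost after worsening, for example a single unfavourable shift applied in both arms and then in each arm alone. For scale, a shift of 0.5 SD for 7 of 28 controls moves the control mean by 7/28 × 0.5 = 0.125 SD.

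The cost is some wording, a few assessments at flexible times and one extra analysis. Recovery will be incomplete: some worsened or admitted patients will be unable to consent or be tested, especially for EEG, which is recorded at the association's headquarters. For PANSS, the sensitivity analysis addresses what is not recovered. The wording should be settled before further follow-up visits pass, because an assessment not made at its visit cannot be obtained later.

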## **2. Main objective**

- To evaluate the impact of a therapeutic dance therapy program on cognitive functions, specifically on memory and executive functions, in patients diagnosed with severe mental disorder by measuring scores on neurocognitive tests such as the BACS and MOCA (subsequently defined in the section on data collection) and by analysing electroencephalographic activity.

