### **3. Data Collection**

The tests will be administered after randomization and before starting the intervention to measure the basal state of each participant and after the completion of the dance therapy program in order to determine the changes generated with the dance therapy program. The tests will also be repeated after 3 months as a follow-up of the results obtained.

All registrations will be done anonymously, assigning each person an identification number. All data will be kept for 5 years.

- **Brief assessment of cognition in schizophrenia (BACS)** (Keefe et al., 2004): serves to quantify cognitive impairment in schizophrenia and/or psychosis. The BACS includes assessments of verbal memory, working memory (Digit Stream), motor speed (Token Motor), verbal fluency, attention and processing speed (Symbol

Coding), and executive function (Tower of London). The minimum and maximum scores on the BACS for each subtest are:

1. Token Motor Task (TMT): The minimum score is 0, and the maximum is 100.
2. List Learning: The minimum score is 0, and the maximum is 50.
3. Digital Sequencing Task: The minimum score is 0, and the maximum is 21.
4. Semantic Fluency: The minimum score is 0, and the maximum is 40.
5. Symbol Coding: The minimum score is 0, and the maximum is 50.
6. Tower of London: The minimum score is 0, and the maximum is 21.
7. Verbal Memory: The minimum score is 0, and the maximum is 20.

These scores are used to evaluate performance on each of the BACS subtests.

Subsequently, it is common to calculate a composite score that summarizes the individual's overall cognitive performance. For the interpretation of results, see the **attached technical sheet**. In our case, all patients in the intervention group will be patients with a diagnosis of psychosis without comorbidities.

- **Montreal Cognitive Assessment (MoCA)** (Ramírez et al., 2014): it is a 30-question test that evaluates mild cognitive dysfunctions by assessing executive function and visuospatial ability, identification, short-term memory, delayed recovery, attention, language, abstraction, animal naming and orientation. The ratings range from 0 to 30 and the cut-off value to determine a normal score is >26 points. The test is administered in about 10-12 minutes.

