In general, these variables provide critical information about the brain's electrical activity. This will allow us to assess associated neurological disorders and the study of the patient's cognition

Therefore, this technique will allow us to identify abnormal patterns of brain activity, evaluate brain responses during resting-state EEG data acquisition, and examine the relationship between activity in different frequency bands and specific cognitive functions. and will allow us to deepen our understanding of brain electrical activity and its correlation with cognitive processes and mental states.

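### A medical finding at an outcome EEG withdraws the patient from the whole study, so a post-programme finding costs a randomised patient the 3-month BACS, MoCA and PANSS

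*Combined protocol and SAP*

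**What the plan says.** Section 2.d of Study Methodology, whose title concerns withdrawal from the study and not only from treatment, includes the criterion "Medical findings, such as epilepsy, during the EEG". It gives one example. It does not say who judges the finding, whether it must be confirmed, which EEG round it applies to, or whether the other assessments go on.

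The EEG belongs to the outcome set. The Main objective is to be met through BACS and MoCA scores and "by analysing electroencephalographic activity". Both groups are tested at baseline, after the programme and 3 months later. Data Collection states: "The tests will also be repeated after 3 months as a follow-up of the results obtained".

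The order of the first tests and random assignment is given in two ways. Workplan says the tests "will be carried out with the 47 patients with SMD to find out their baseline status. The people with SMD will be randomly assigned", so testing comes first. Data Collection says: "The tests will be administered after randomization and before starting the intervention".

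The statistical analysis section plans mixed models for the repeated measurements. It names no analysis population, no missing-data rule and no follow-up of withdrawn patients.

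**The concern.** An EEG finding may be a reason to refer a patient, to stop the dance sessions or to make no further recordings. It does not prevent a cognitive test or a symptom rating at a visit that is already in the calendar. Under the rule as written, such a finding ends the patient's participation altogether. If it comes after random assignment, this is an exclusion after allocation. It rests on an unconfirmed observation made while an outcome was being measured, and it could be avoided at no cost in visits. What is at stake is outcome data on randomised patients, chiefly at 3 months.

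**Working it through.** The plan states no figure on this point, so there is none to reproduce. The loss follows from the visit schedule.

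**Inputs**
- Post-baseline visits: 2, after the programme and at 3 months (Design; Data Collection).
- Instruments other than EEG at each visit: 3, namely BACS, MoCA and PANSS (Workplan; Data Collection).
- Arm sizes: 26 and 21 (Design), or 28 per group (Sample size calculation).
- Assumption 1: withdrawal from the study ends later assessments. No section says so outright, but it is the ordinary meaning and nothing provides otherwise.
- Assumption 2: the remaining tests of the visit at which the finding occurs are completed.

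**Assessments lost per withdrawn patient**

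Scheduled post-baseline assessments: 2 visits × 3 instruments = 6.

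| EEG with the finding | Tests after randomisation (Data Collection) | Tests before assignment (Workplan) |
|---|---|---|
| First | 6/6 = 100% | no randomised patient lost (screening) |
| Post-programme | 3/6 = 50% | 3/6 = 50% |
| 3 months | 0/6 = 0% | 0/6 = 0% |

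The post-programme row is the same in both columns, so that loss does not depend on how the conflict is settled. The 100% entry exists only if testing follows randomisation.

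**Weight of one patient at a lost visit**
- Dance arm: 1/26 = 3.8%.
- Control arm: 1/21 = 4.8%.
- Either arm, if 28 per group are assigned: 1/28 = 3.6%.

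**Does it matter for power?** The documents give no rate of EEG findings, so the rates below are assumptions that only show a range. Take the plan's planning values at face value: a difference of 2 (reading its minimum response as 2 units), SDs 2.822 and 2.588, one-sided alpha 0.05, and 26 versus 21 patients.
- Combined SD = √((2.822² + 2.588²)/2) = 2.71.
- Power = Φ(2 / (2.71 × √(1/26 + 1/21)) − 1.645) = 0.809.
- Reducing both arms by the assumed share withdrawn in one EEG round:

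| Assumed rate | Expected withdrawals of 47 | Power |
|---|---|---|
| 1% | 0.47 | 0.805 |
| 2% | 0.94 | 0.802 |
| 5% | 2.35 | 0.791 |
| 10% | 4.7 | 0.771 |

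At rates up to 5% the change is under 0.02. This does not support a claim about power.

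**The case against.** The strongest case against has five parts.

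- **It applies the exclusion criteria.** Section 2.c already rules out epileptic seizures and any "neurological disorder that may function as a confounding factor". A finding at the first EEG precedes the intervention, cannot be caused by it, and mostly reveals ineligibility. This stands for the first EEG and is a good reason to place that recording before randomisation. It does not justify ending cognitive follow-up of a patient who has completed the programme period.
- **The criterion is clearer than alleged.** Its example is a diagnosis, and read with section 2.c it plausibly means a neurological condition. That is fair, but there is still no confirmation step. A reader might go further and link the rule to the analysis section's statement that "this technique will allow us to identify abnormal patterns of brain activity", inferring that any unusual spectrum triggers withdrawal. The documents do not support that. The sentence describes what spectral analysis can do, and nothing connects it to section 2.d.
- **The counts only restate the schedule.** Anyone who leaves at that time, for any reason, loses the same visits. This is true. The difference is that this departure is imposed by the protocol and is avoidable.
- **Existing provisions absorb it.** The 10% and 25% loss allowances may cover these patients, no section says collected data are deleted, and mixed models can use earlier visits. All of this stands and limits the size. A model still cannot use scores that were never collected.
- **The target is narrow.** Withdrawal for worsening symptoms or hospital admission leaves the same gap in follow-up. That is correct, and it is a separate matter that this change does not settle.

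**Conclusion.** The point holds as a minor matter and a cheap improvement. On either order of testing and assignment, a finding at the post-programme EEG loses that randomised patient's 3-month BACS, MoCA and PANSS (3 of 6 post-baseline assessments), although the visit is already scheduled. A first-EEG finding loses both later visits only on the order in Data Collection. A 3-month finding loses nothing.

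A reader might infer that the rule biases the comparison or undermines power. The documents do not support either. The rule covers both arms, no difference between arms is shown, no frequency is given, and the loss allowances may already cover these patients. The number affected is probably small.

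The conclusion rests on reading withdrawal from the study as the end of assessment, and on the tests of the visit in question being completed.

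**What to change.** 1. Follow the order in Workplan: first EEG, then randomisation. Handle a finding at that EEG as screening under section 2.c, and align Data Collection with this.
2. Reword the EEG criterion in section 2.d. A finding after randomisation leads to referral to the treating unit and, if that unit advises, to stopping dance sessions or further EEGs. It is not a ground for leaving the study. Consenting patients continue the scheduled BACS, MoCA and PANSS visits and are analysed as randomised.
3. Add to the statistical analysis section one sensitivity analysis of BACS, MoCA and PANSS that leaves out patients with a confirmed neurological disorder covered by section 2.c.

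How abnormal recordings are treated within the EEG analysis itself remains for the sponsor to decide.

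The cost is one reworded criterion, one aligned sentence on test order and one extra analysis, with no new tests or visits. The downside is that a few patients whom section 2.c would have excluded stay in the main cognitive and symptom analysis. The sensitivity analysis shows whether they matter.
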